## **6.7 Concomitant Antibiotic Therapies**

Concomitant antibiotic therapies will be determined by Botanix prior to database lock.

Counts and percentages will be provided to summarize the use of concomitant antibiotic therapies reported throughout the study. The number and percent of subjects who took concomitant therapies will be shown by ATC level 2 term and preferred name.

A by-subject listing of all concomitant antibiotic therapies will be presented.

## **6.8 Analysis of Efficacy**

The efficacy analyses will be performed using the ITT (primary), mITT (supportive), and PP (supportive) populations. The IGA, total BSA affected by AD, Signs of AD total score, and I-NRS analyses will employ the methods for handling missing data as described in Section 6.1.5. IGA, total BSA affected by AD, Signs of AD score, and I-NRS data will also be shown in by-subject listings.

### **6.8.1 Primary Efficacy Analysis**

The proportion of subjects with IGA success defined as an IGA score of Clear (0) or Almost Clear (1) with at least a 2-grade improvement from Baseline at Day 85 will be analyzed using logistic regression with a term for treatment.

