4. STUDY ENROLLMENT AND WITHDRAWAL

4.1. Inclusion Criteria

To be included in the study, subjects must meet the following inclusion criteria.

1. Subject is of either gender between 12 and 70 years of age, inclusive.
2. Subject (or parent/legal guardian) has the ability and willingness to sign a written informed consent.
3. Subject has a diagnosis of chronic (≥ 1 year), stable atopic dermatitis (AD) according to Hanifin and Rajka [Hannifin 1980]
4. Subject has $\geq 5\%$ and $\leq 30\%$ body surface area (BSA) of AD involvement excluding the scalp and groin.
5. Subject has an Investigator's Global Assessment (IGA) score of moderate (3) atopic dermatitis on the 5-point IGA (0-4) scale.
6. For selected photography sites, subject has a target lesion 25 to 200 cm² in surface area on the trunk, upper extremities or lower extremities with a Baseline Signs of AD score of ≥ 6 and ≤ 12 .
7. Subject is in good general health without clinically significant hematological, cardiac, respiratory, renal, endocrine, gastrointestinal, psychiatric, hepatic, or malignant disease, as determined by the investigator.
8. Subject has suitable venous access for blood sampling.
9. Subject is able and willing to complete the study and to comply with all study instructions and attend the necessary visits.
10. Male subjects and their partners must agree and commit to use a barrier method of contraception throughout the study and for 90 days after last study drug application.
11. A negative urine pregnancy test (UPT) result for all WOCBP at the Screening Visit and Baseline Visit. A WOCBP is one who is not permanently sterilized or not postmenopausal. Postmenopausal is defined as 12 months with no menses without an alternative medical cause.
12. Sexually active women must agree to use the following throughout the study and for 30 days after last study drug application. WOCBP who are not sexually active at Baseline and become sexually active must identify a plan for contraception.
 - a. One of these highly effective contraception methods
 - i. Intrauterine device (IUD); hormonal (injections, implants, transdermal patch, vaginal ring; tubal ligation; partner vasectomy, OR
 - b. Oral contraceptives WITH a barrier method (listed below), OR
 - c. Two barrier forms of contraception (listed below)
 - i. Male or female condom; diaphragm; cervical cap; contraceptive sponge.

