4.2. Exclusion Criteria

If a subject meets any of the following exclusion criteria, they may not participate in the study.

1. Female subject who is breast feeding, pregnant, or planning to become pregnant.
2. Subject who has an IGA score of 2 (mild) or 4 (severe).
3. Subject with history of known or suspected intolerance to the drug product excipients (hexamethyldisiloxane, polypropylene glycol (PPG) 15 stearyl ether, silicone gum, and isopropyl alcohol).
4. Subject has any clinically significant active infection in the investigator's opinion. This includes active impetigo at any AD lesion.
5. Subject has known Hepatitis-B, Hepatitis-C, or HIV infection.
6. Subject has excessive body or facial hair that would interfere with the evaluation of safety or with the diagnosis or assessment of AD.
7. Subject has sunburns, unevenness in skin tones, tattoos, scars, excessive hair, freckles, birthmarks, moles, or other skin damage or abnormality that would result in the inability to evaluate the AD lesions.
8. Subject has clinically significant or severe allergies that in the investigator's opinion would interfere with participation in the study.
9. Subject has known intolerability to topical treatments e.g., reports excessive burning/stinging or pain with use of topical treatments.
10. Subject has an active or potentially recurring skin conditions(s) other than AD that in the investigator's opinion would interfere with participation in the study.
11. Subject has unstable AD consistent with a requirement for high-potency corticosteroids.
12. Subject has used dupilumab (Dupixent) within 12 weeks prior to the Baseline Visit.
13. Subject has used any biologic therapy, other than dupilumab, within 28 days prior to the Baseline Visit.
14. Subject has used systemic (oral, IV or IM) corticosteroids within 28 days prior to the Baseline Visit. Intra-articular injection for arthroses allowed.
15. Subject has used topical anti-pruritics (e.g., PDE4 inhibitors) within 28 days prior to the Baseline Visit.
16. If subject is taking oral antihistamines, subject has not been on a stable dose of oral antihistamines within 28 days prior to the Baseline visit.
17. Subject has used phototherapy, tanning beds, or any other artificial light device within 28 days prior to the Baseline Visit.
18. Subject has used topical corticosteroids within 14 days prior to the Baseline Visit.
19. Subject has used topical calcineurin inhibitors within 14 days prior to the Baseline Visit.

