9.3.3. Efficacy Analyses

The efficacy variables include the IGA, BSA of AD, Signs of AD score, EASI score, and pruritus scores (I-NRS) collected at Screening/Baseline and all subsequent study visits and the WI-NRS recorded daily by subjects.

The primary efficacy endpoint for the study is the proportion of subjects with IGA success defined as an IGA score of Clear (0) or Almost Clear (1) with at least a 2-grade improvement from Baseline at Day 85. The IGA will be dichotomized into “success” and “failure” at study Day 15, Day 29, Day 57, and Day 85. Success on IGA defined as a score of Clear (0) or Almost Clear (1) and at least a 2-grade improvement from Baseline at Day 15, Day 29, Day 57, and Day 85 will be analyzed using logistic regression, adjusting for Baseline IGA.

Summary statistics will be prepared for the change from Baseline in the percent of BSA affected by AD at Days 15, 29, 57, and 85. The change from Baseline in BSA of AD will be analyzed using ANCOVA with Baseline BSA of AD and treatment as covariates.

Summary statistics will be presented for the change from baseline in each of the Signs of AD scores (erythema, exudation, excoriation, induration/papulation, and lichenification) at each timepoint (Day 15, Day 29, Day 57 and Day 85). A total score will be calculated based on the sum of each of the Signs of AD (0, 1, 2, or 3; max score of 15) and the change from baseline will be summarized for each timepoint. The change from baseline in Signs of AD score at Day 15, Day 29, Day 57, and Day 85 will be analyzed using ANCOVA with Baseline Signs of AD score and treatment as covariates.

The proportion of subjects with an EASI 50 and EASI 75 score will be summarized at Day 15, Day 29, Day 57, and Day 85 and compared using logistic regression, adjusting for Baseline EASI score. Summary statistics will be prepared for the change from Baseline in the EASI score and I-NRS at each timepoint (Day 15, Day 29, Day 57 and Day 85).

Summary statistics will be prepared for the change from Baseline in the Signs of AD score for the target lesion (selected sites) at each timepoint (Day 15, Day 29, Day 57 and Day 85).

Summaries of the pruritus scores (WI-NRS) reported by the subjects in the daily Patient Diary will be presented using daily means by treatment and with graphic presentations.

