12.1.2. Protocol Deviations

A protocol deviation is any noncompliance with the clinical trial protocol, GCP, or other study requirements (e.g., SOPs, Laboratory Manuals, etc). The noncompliance may be either on the part of the subject, the investigator, or the study site staff. As a result of deviations, corrective actions are to be developed by the site and implemented promptly.

These practices are consistent with ICH E6:

- 4.5 Compliance with Protocol, sections 4.5.1, 4.5.2, and 4.5.3
- 5.1 Quality Assurance and Quality Control, section 5.1.1

- 5.20 Noncompliance, sections 5.20.1, and 5.20.2.

It is the responsibility of the site to use continuous vigilance to identify and report deviations within 5 working days of identification of the protocol deviation, or within 5 working days of the scheduled protocol-required activity. All deviations must be addressed in study source documents and reported to the clinical study monitor or to the CRO. Protocol deviations must be sent to the IRB/EC per their guidelines. The site investigator/study staff is responsible for knowing and adhering to their IRB/EC requirements.

It is not anticipated that waivers of eligibility requirements will be granted for any subjects. However, if eligibility requirements are waived in special circumstances, waivers must be approved by the medical monitor and the sponsor before a subject may be enrolled. Documentation of granted waivers will be maintained in the investigator's and sponsor's files.

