#### **4.1.2 Method of Assigning Subjects to Treatment Groups**

A randomization schedule will be generated by a statistician(s) from QST Consultations, Ltd. (QST) Statistical Services department who is not associated with the day-to-day conduct of the study, using a validated system. The randomization list will not be stratified, but stratification by site will be accomplished within the IWRS.

Once a subject is deemed eligible to enroll, randomization will occur using an IWRS. The IWRS will assign a study drug kit number based on a predetermined randomization schedule. The kit number will be recorded in the electronic case report form (eCRF). Randomization will be 1:1 (100 active: 100 vehicle).

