## **8. CHANGES IN THE PLANNED ANALYSES**

Baseline IGA will not be used as a factor for the primary, secondary, and exploratory efficacy IGA endpoints as treatment was not stratified by IGA score.

The ITT population was updated to specify inclusion only of subjects with at least one post-Baseline efficacy assessment.

The mITT population was added to the SAP in order to assess efficacy for subjects with consistent areas of AD lesions.

A tipping point analysis was added as an additional sensitivity analysis on the ITT population.

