Failure	xx ( xx.x%)	xx ( xx.x%)
Age: 18 to < 30 Years		
	BTX 1204 4% BID (N=xxx)	Vehicle BID (N=xxx)
At Least a 2 Grade Improvement from Baseline and IGA Grade of 0 or 1		
n	xx	xx
Success	xx ( xx.x%)	xx ( xx.x%)
Failure	xx ( xx.x%)	xx ( xx.x%)
Age: ≥ 30 Years		
	BTX 1204 4% BID (N=xxx)	Vehicle BID (N=xxx)
At Least a 2 Grade Improvement from Baseline and IGA Grade of 0 or 1		
n	xx	xx
Success	xx ( xx.x%)	xx ( xx.x%)
Failure	xx ( xx.x%)	xx ( xx.x%)

Note: No imputations were made for missing data.

SOURCE: USERNAME\SPONSOR\PROJECT\JOBNAME (DATE, TIME)

Repeat Table 14.2.1.6 for the following:

Table 14.2.1.7: Subgroup Summary of the Primary Endpoint: Dichotomized IGA Success at Day 85 (PP Population)

Table 14.2.2.1.1: Secondary Endpoint: Change from Baseline in Signs of AD Total Score at Day 85  
(ITT Population)

	BTX 1204 4% BID (N=xxx)	Vehicle BID (N=xxx)	Treatment P-Value
Change from Baseline in Total Signs of AD			
n	xx	xx	
Mean	xx.x	xx.x	
SD	xx.xx	xx.xx	
Median	xx.x	xx.x	
Min., Max.	xx, xx	xx, xx	
LSMean a	xx.x		x.xxx a
LSSD a	xx.xx		

a Least squares mean, standard deviation, and p-value from an analysis of covariance with baseline Total Signs of AD and treatment as covariates.

Note: Missing values imputed using LOCF.

SOURCE: USERNAME/SPONSOR/PROJECT/JOBNAME (DATE, TIME)

Repeat Table 14.2.2.1.1 for the following:

Table 14.2.2.1.2: Secondary Endpoint: Change from Baseline in Signs of AD Total Score at Day 85 (mITT Population)

Table 14.2.2.1.3: Secondary Endpoint: Change from Baseline in Signs of AD Total Score at Day 85 (PP Population)

**Programming note:** *Replace last footnote with* - Note: No imputations were made for missing data.

Table 14.2.2.2.1: Secondary Endpoint: Dichotomized IGA at Day 85  
(ITT Population)

	BTX 1204 4% BID (N=xxx)	Vehicle BID (N=xxx)	Treatment P-Value a
IGA Grade of 0 or 1			
n	xx	xx	
Success	xx ( xx.x%)	xx ( xx.x%)	
Failure	xx ( xx.x%)	xx ( xx.x%)	
Success a	xx.x%	xx.x%	x.xxx
Failure a	xx.x%	xx.x%	
At Least a 2 Grade Improvement from Baseline in IGA			
n	xx	xx	
Success	xx ( xx.x%)	xx ( xx.x%)	
Failure	xx ( xx.x%)	xx ( xx.x%)	
Success a	xx.x%	xx.x%	x.xxx
Failure a	xx.x%	xx.x%	

a Estimates and p-value from a logistic regression with a term for treatment group and adjusted for baseline IGA.

Note: Missing values imputed using LOCF.

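### Every eligible subject has Baseline IGA 3, so the protocol's covariate for IGA success adjusts nothing; the SAP drops it for the wrong reason and names no baseline covariate that varies

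*SAP*

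**What the plan says.** Protocol 9.3.3 says that IGA success at each post-baseline visit "will be analyzed using logistic regression, adjusting for Baseline IGA". No other covariate is named for that model. Inclusion criterion 5 (Protocol 4.1) requires a "score of moderate (3) atopic dermatitis on the 5-point IGA (0-4) scale", and exclusion criterion 2 (Protocol 4.2) bars grades 2 and 4. Eligibility waivers are not expected, but Protocol 12.1.2 leaves a route: "if eligibility requirements are waived in special circumstances, waivers must be approved by the medical monitor and the sponsor".

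SAP 6.8.1 fits a simpler model: IGA success "will be analyzed using logistic regression with a term for treatment". SAP Section 8 explains the change, the stratification in question being on IGA grade: "Baseline IGA will not be used as a factor for the primary, secondary, and exploratory efficacy IGA endpoints as treatment was not stratified". SAP 6.1.4 confines baseline BSA and baseline Signs of AD to the models for their own change scores and rules out further covariates. Under SAP 4.1.2, "stratification by site will be accomplished within the IWRS", but site is not in the primary model.

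The shells are not consistent. The footnote to the primary table (14.2.1.1) names treatment only. The footnotes to Tables 14.2.2.2.1 and 14.2.3.5.1, for the secondary and exploratory IGA endpoints, still read "Estimates and p-value from a logistic regression with a term for treatment group and adjusted for baseline IGA".

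**The concern.** A baseline covariate helps a responder analysis only if it varies between subjects and predicts the outcome. The protocol chose one that eligibility holds fixed. The SAP removed it without recognising this, so whether another baseline measure should take its place is never discussed.

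At stake are some precision in the primary comparison and protection against a chance imbalance in baseline severity. Both are available from data already collected. Separately, a programmer following the shells would fit a model that SAP 6.1.4 and Section 8 exclude.

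**Working it through.** **1. The protocol model reduces to the SAP model.** Write logit P(success) = a + b × treatment + c × IGA. With IGA = 3 for everyone this is (a + 3c) + b × treatment. Only the sum a + 3c can be estimated. A numerical check of the design matrix (intercept, treatment, IGA = 3) gives rank 2 for 3 columns. The estimate of b and its standard error are those of the treatment-only model. An eligibility waiver or deviation is the only way to obtain a second IGA value.

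**2. The reason in Section 8 conflicts with the SAP's own practice.** Baseline BSA (SAP 6.8.2.4) and baseline Signs (SAP 6.8.2.1) are ANCOVA covariates, and neither is a stratification factor. Site is the stratification factor and is left out. So stratification is not the rule that decides which covariates the SAP uses.

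**3. Severity can still vary within grade 3.** Inclusion criterion 4 allows BSA from 5% to 30%, a sixfold range. The notes to the IGA table (Protocol 6.1, Table 2) place marked signs of limited extent in grade 3. BSA and Signs are both recorded by the Baseline Visit. For EASI 50 and EASI 75, Protocol 9.3.3 does adjust a responder model for baseline severity. The documents do not say how strongly BSA or Signs predict IGA success.

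**4. Power.** The plan has no power figure to reproduce; 100 per arm rests on clinical considerations. Assumptions here: two-sided 0.05 and success rates of 15% and 30%. A second pair, 18.2% and 34.8%, borrows the Phase 1b figures, which belong to a different endpoint at 4 weeks.

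Normal approximation: power = Φ{[d√n − 1.96√(2p̄q̄)] / √(p₀q₀ + p₁q₁)}. For 15% vs 30%: d√n = 0.15 × 10 = 1.5; 1.96 × √(2 × 0.225 × 0.775) = 1.157; the denominator is √(0.1275 + 0.21) = 0.581. Power = Φ(0.343/0.581) = Φ(0.59) = 72.2%. For 18.2% vs 34.8% the same formula gives 76.2%.

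Simulation: 4,000 trials per cell, Wald test, one normally distributed baseline covariate, marginal rates held fixed. The Monte Carlo standard error of each power is about √(0.72 × 0.28/4000) = 0.7 points.

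| Odds ratio per SD (assumed) | 15% vs 30%: unadjusted, adjusted | 18.2% vs 34.8%: unadjusted, adjusted |
|---|---|---|
| 1.0 | 71.8%, 71.5% | 76.3%, 75.9% |
| 1.5 | 72.2%, 73.3% | 76.1%, 77.2% |
| 2.0 | 73.6%, 76.4% | 77.4%, 81.1% |
| 3.0 | 71.5%, 79.9% | 76.9%, 84.0% |

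At 15% vs 30% the gain runs from −0.3 points (noise) to 79.9 − 71.5 = 8.4 points. With 20% in both arms, type I error was 4.6% to 5.5% across both models. With two covariates at 15% vs 30%, power went from 71.7% to 71.4% when they were uninformative and from 71.1% to 77.5% at an odds ratio of 3 per SD, with type I error of 4.4% to 5.2%.

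**5. Chance imbalance.** With 100 per arm the standardised baseline difference has SD √(2/100) = 0.14, so differences up to 1.96 × 0.14 = 0.28 SD are ordinary. At an assumed odds ratio of 2 per SD, such a difference shifts the treatment log odds ratio by roughly 0.28 × ln 2 = 0.19. The log odds ratio for 30% vs 15% is ln[(0.30/0.70)/(0.15/0.85)] = 0.89.

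**6. Site as a fixed effect.** The documents give no number of sites. Suppose 20 equal sites of 10 subjects and 15% success. The chance that a given site has no success is 0.85^10 = 0.197. The chance that at least one of the 20 has none is 1 − (1 − 0.197)^20 = 98.8%. Each such site has a coefficient that diverges.

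**The case against.** The strongest reply is that nothing has been lost. Removing a constant changes no estimate, the removal is disclosed, and SAP 6.1.4 states openly that no other covariates are planned. Under 1:1 randomisation the treatment-only test is valid and targets the difference in proportions that the endpoint describes. The nominal error rate already allows for chance imbalance on average. Tests are declared exploratory (Protocol 9.3.7, SAP 6.1.8), Protocol 9.2 disclaims hypothesis testing, and there is no power target to miss. The gain depends on an assumed prognostic strength, and restricting entry to one IGA grade may narrow the spread of severity. Covariates in a logistic model also turn the odds ratio from marginal to conditional.

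Most of this stands. It rules out two readings that a reader might infer. One is that the SAP weakened an adjusted protocol analysis; step 1 shows there was no working adjustment to weaken. The other is that the unadjusted primary result would be biased or have an inflated error rate; the simulations do not show that. It is also tempting to conclude that site must enter the model because randomisation is stratified by it. Step 6 shows why unpooled site terms could leave the model unstable.

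What the reply does not answer is that the stated reason is wrong, that the possibility of a replacement was not considered, and that adjustment cost essentially no power when the covariate was uninformative. The change of estimand is met by reporting a standardised difference in proportions.

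**Conclusion.** The point holds as a matter of efficiency and documentation. Baseline IGA is constant by eligibility, the SAP drops it for a reason that does not justify the change, and no varying baseline measure replaces it. Under assumed rates of 15% and 30% with 100 per arm, adjustment is worth about 0 to 8 points of power. Where in that range the trial falls depends on how well baseline BSA and Signs predict IGA success, which the documents do not show.

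The stale footnotes contradict SAP 6.1.4 and Section 8. A reader might take them to put the primary result in doubt, but the primary shell is correct and the footnotes name a constant, so barring waivers or deviations they change no estimate. The change is worth making because it needs no new data, but the trial remains valid without it.

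**What to change.** Amend the SAP before unblinding:

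- In SAP 6.8.1 and the other IGA logistic models, prespecify treatment, baseline total BSA and baseline Signs of AD total score, and amend 6.1.4 to match.
- Report the covariate-standardised difference in success proportions with a 95% CI, for example by g-computation with delta-method or bootstrap variance. State this as the estimand and say which test gives the reported p-value.
- Keep the treatment-only model as a sensitivity analysis.
- Do not add fixed site effects by default. Reflect the site stratification through a prespecified pooled factor, for example the US vs AUS/NZ region split already defined in SAP 6.1.11, or through a site-stratified Mantel-Haenszel sensitivity analysis.
- Remove the Baseline IGA adjustment from the footnotes to Tables 14.2.2.2.1 and 14.2.3.5.1 and their mITT and PP repeats.
- In Section 8, give the actual reason: Baseline IGA does not vary among eligible subjects.

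The cost is SAP and shell wording, rows for the difference and its CI in the IGA tables, and a modest amount of programming. No new data are needed.

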## **6.8.2 Secondary Efficacy Analysis**

### **6.8.2.1 Signs of Atopic Dermatitis at Day 85**

The Signs of AD total score will be calculated based on the sum of the score for each component (erythema, exudation, excoriation, induration/papulation, and lichenification). Each component will be scored as 0, 1, 2, or 3. The total score therefore ranges from 0 to a maximum score of 15.

The change from Baseline to Day 85 in the total Signs of AD score will be analyzed using analysis of covariance (ANCOVA) with Baseline Signs of AD as covariate and treatment as a factor.

### **6.8.2.2 Proportion of Subjects with an IGA of Clear (0) or Almost Clear (1) at Day 85**

The proportion of subjects with an IGA of Clear (0) or Almost Clear (1) at Day 85 will be analyzed analogously to the primary endpoint.

### **6.8.2.3 Proportion of Subjects with at least a 2-Grade Improvement in IGA at Day 85**

The proportion of subjects with at least a 2-grade improvement from Baseline at Day 85 will be analyzed analogously to the primary endpoint.

### **6.8.2.4 Percent of Total Body Surface Area Affected by Atopic Dermatitis at Day 85**

The change from Baseline to Day 85 in percent of total BSA affected by AD will be analyzed using ANCOVA with Baseline total BSA affected by AD as covariate and treatment as a factor.

